Interventions to Promote Healthy Lifestyle and Academic Performance in Children During the Summer Months.

NCT03321071

June 4th, 2020

Methods

Trial Design

This study is a three-armed quasi-experimental study employing a repeated measure within and between participant design comparing the HSL (n=60), to 21C (n=60), and no program (n=60). HSL is designed to mitigate academic learning loss and accelerated summer BMI gain by positively impacting children's obesogenic behaviors.

Participants

To distribute the costs of operating HSL the study takes place over two summers (i.e., June-August, 2018 & 2019). A single elementary school in the Columbia, SC metropolitan area will participate each summer (i.e., two schools, one each summer). Schools will be selected because they serve children from low-income households (100% free and reduced priced lunch) and they operate a 21C summer program. Inclusion criteria are that children are in the 2nd, 3rd, or 4th grade and their standardized reading score on the Measures of Academic Progress is between the 25th and the 75th percentile. Exclusion criteria is the presence of a severe intellectual disability (e.g., fragile X syndrome, severe autism). Measures of Academic Progress scores between the 25th and the 75th percentile and the absence of a severe intellectual disability were chosen as inclusion/exclusion criteria because these are the criteria the school district used to select children to participate in the 21C. A total of 90 students will participate each summer (i.e., 180 participants total). Participants will be assigned to one of three conditions HSL (n=60), 21C (n=60), or no program (n=60).

Interventions

HSL was designed in partnership with the local school district in which the study will occur. HSL was designed to, (1) address summer declines in reading achievement and (2) mitigate accelerated unhealthy weight gain during the summer by positively impacting children's obesogenic behaviors. HSL will operate at the participating schools and will be delivered by certified teachers. Participants enrolled in HSL will attend daily (Monday-Thursday, 8:00-15:30) for six weeks during the summer, with a one-week break in the middle of the program (i.e., 4th of July). The program day will consist of alternating sixty-minute periods of physical activity (3

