Follow-up assessments will be conducted 3-months following baseline. For Physical Activity, Sleep, Screen Time, and Diet measures will be collected continuously from baseline to outcome.

Body Mass Index – Primary Outcome. Following standardized protocols trained research assistants will collect children's heights (nearest 0.1 cm) and weights (nearest 0.01 lbs.) without shoes in light clothing using a portable stadiometer (Model S100, Ayrton Corp., Prior Lake, Minn.) and digital scale (Healthometer model 500KL, Health o meter, McCook, Ill.). BMI will be calculated ($BMI = \text{kg}/\text{m}^2$) and transformed into age and sex specific z-scores (zBMI) according to the Centers for Disease Control growth charts [2].

Measures of Academic Progress Reading Scores – Primary Outcome. Children's reading achievement will be assessed via the MAP reading assessment. Created by the Northwest Evaluation Association (www.nwea.org), MAP results are widely accepted and used extensively in school-aged children [3]. Scores are reported using the Rasch Unit Scale, a curriculum scale developed using Item Response Theory that estimates student achievement. The Rasch Unit Scale ranges from 140-300 and are norm referenced based on grade [3]. MAP reading assessment will be administered as part of typical curriculum in the fall (first month of school) and end of the spring (last month of school) of each year.

Cardiorespiratory Fitness – Secondary Outcome. The Progressive Aerobic Cardiovascular Endurance Run (PACER) will be administered during regularly scheduled PE [4-10]. The PACER will be carried out by a trained research assistant and the PE teacher following standardized protocols on a marked outdoor green space.

Physical Activity & Sleep – Physical activity (MVPA, sedentary time) and sleep (total sleep duration, sleep onset, sleep offset, midpoint) will be measured using a Fitbit Charge 2TM (Fitbit Inc., San Francisco, California, USA). Fitbit Charge 2 devices have demonstrated initial reliability and validity for detecting heartrate and sleep [11-13]. Each Fitbit will be assigned a unique numeric identifier and each device will be linked to Fitabase (San Diego, CA, USA) a web-based interface that allows remote access and download of participants' second level

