Diet will be assessed via parent report food screener[21]. Items will be scored by four possible response categories and responses consist of the following: 0 ('child did not consume'), 1 ('child consumed a little'), 2 ('child consumed some'), and 3 ('child consumed a lot') with those individual items. Individual food items will be grouped in accordance with the Healthy Meal Index (HMI) [22]. Food categories include; fruits, vegetables, dairy (non-sugar based), convenience foods, sweets and desserts and sugar sweetened beverages. Consumption will be dichotomized (i.e., 'did' vs. 'did not' consume) and reported as mean days/week [21]. Two variables will be created for analysis of diet; healthy foods/drinks (fruits, vegetables, and dairy), unhealthy foods/drinks (convenience foods, and sweets/desserts, sugar sweetened beverages).

Sample Size

The above selection criteria will yield 60 children in each arm of the study. Previous studies have shown that samples of 60-100 participants provide reliable estimates of statistical and recruitment parameters upon which subsequent large-scale trials can be based [23].

Randomization

A total of 180 children will be randomly selected to participate in the study. Of the 180 children, 60 will be enrolled in 21C program. Children will not randomly assigned to the 21C program as the participating school declined random assignment of these children. The remaining 120 (i.e., n=60 in 2018 and n=60 in 2019) will randomly allocated to one of two conditions HSL or control (no program) using a random number generator. Random assignment will be completed by the study principal investigator who will not be involved in data collection and will be completed each summer after participants enrolled in the study using the runiform command in Stata (v14.2, College Station, TX). Once implemented randomization cannot be changed.

Data Analysis

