All analyses will be completed using Stata (v14.2, College Station, TX) with α levels set to $P < 0.05$. Data will be assessed for normality and descriptive statistics of programs, child characteristics, and outcome variables at baseline. The analyses will be estimated using an intent-to-treat approach [24, 25]. Multilevel mixed effects linear regressions with measures nested within children will be estimated. Separate models will be estimated for each dependent variable and included dummed group (control, HSL, 21C), time (baseline, post-summer, post schoolyear), and all group-x-time interactions. All analyses will include baseline scores on the dependent variable, age, gender, race, and year of participation as covariates in the models. Missing data will be handled using full information maximum likelihood estimates [26, 27]. The Benjamini-Hochberg procedure with a false discovery rate of 10% will be utilized to account for multiple comparisons [28].

1. *The Effect of Nutrition Education on Third Graders' School Lunch Consumption in a School Offering Food Pyramid Choice Menus.* 1998. p. 34.
2. Kuczmarski, R., et al., *CDC growth charts for the US: methods and development.* Vital Health Stat, 2002. **11**(246): p. 1-190.
3. Thum Y. M. and C.H. Hauser, *NWEA 2015 MAP Norms for Student and School Achievement Status and Growth*, in *NWEA Research Report*. 2015, NWEA: Portland, OR.
4. Welk, G. and M.D. Meredith, *Fitnessgram and Activitygram Test Administration Manual-Updated 4th Edition*. 2010: Human Kinetics.
5. Tomkinson, G.R., et al., *Secular trends in the performance of children and adolescents (1980–2000)*. Sports Medicine, 2003. **33**(4): p. 285-300.
6. Beets, M.W. and K.H. Pitetti, *One-mile run/walk and body mass index of an ethnically diverse sample of youth*. Medicine and Science in Sports and Exercise, 2004. **36**(10): p. 1796-1803.
7. Beets, M.W. and K.H. Pitetti, *A Comparison of 20-M Shuttle-Run Performance of us Midwestern Youth to Their National and International Counterparts*. Pediatric Exercise Science, 2004. **16**(2): p. 94-112.
8. Beets, M.W., K.H. Pitetti, and B.J. Cardinal, *Progressive aerobic cardiovascular endurance run and body mass index among an ethnically diverse sample of 10-15-year-olds*. Research Quarterly for Exercise and Sport, 2005. **76**(4): p. 389-397.

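### Does leaving the Benjamini-Hochberg family undefined make the randomised HSL-control result unsafe?

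*Combined protocol and SAP*

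**What the plan says.** The Data Analysis section has one sentence on multiplicity: "The Benjamini-Hochberg procedure with a false discovery rate of 10% will be utilized to account for multiple comparisons [28". The same paragraph runs all analyses "with α levels set to $P < 0.05" and fits one model per outcome with "dummed group (control, HSL, 21C), time (baseline, post-summer, post schoolyear), and all group-x-time interactions".

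The Outcomes section labels two outcomes as primary: "Body Mass Index – Primary Outcome" and "Measures of Academic Progress Reading Scores – Primary Outcome". Fitness is labelled secondary. The activity, sleep, screen time and diet measures carry no label.

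Trial Design describes the study as "comparing the HSL (n=60), to 21C (n=60), and no program (n=60" per arm. Under Randomization, only HSL and control are allocated at random; for the third arm, "Children will not randomly assigned to the 21C program as the participating school declined random assignment of these children".

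The Sample Size section gives no power calculation. It relies on the argument that samples of this size "provide reliable estimates of statistical and recruitment parameters upon which subsequent large-scale trials can be based".

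**The concern.** Benjamini-Hochberg cannot be run without a list of tests, because the cut-off for the i-th smallest of m p-values is 0.10 × i/m. The plan gives neither m nor the list. Fitting a separate model for each outcome does not define a family.

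Keeping the two primaries apart from the other outcomes would not settle the matter. With three groups, a primary family could hold HSL-control only (two tests), three pairs within each outcome (three tests, twice) or all pairs on both outcomes (six tests).

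The procedure is also step-up, so every rejection of a 21C comparison loosens the cut-off for HSL-control, the one randomised contrast. Differences involving 21C may partly reflect selection. A borderline zBMI or reading result for HSL against control might then be read either way, with an unclear error rate. The document is dated after both intervention summers, so the family could in principle be chosen with results in hand.

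**Working it through.** **Inputs from the document.** False discovery rate 10% and level 0.05 (Data Analysis); 60 per arm (Sample Size); three groups (Data Analysis); two primaries (Outcomes). The 10% is a chosen level, so there is no derived figure to reproduce.

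**Assumptions, not in the document.** Normal change scores with SD 1, independent outcomes, one post-summer comparison, two-sided tests. 21C differs from both other arms by d SD. Pairwise z-statistics have standard error √(2/60).

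**1. Cut-offs, 0.10 × i/m.**

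- m = 2: 0.05, 0.10
- m = 3: 0.0333, 0.0667, 0.10
- m = 6: 0.0167, 0.0333, 0.05, 0.0667, 0.0833, 0.10

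An HSL-control p of 0.0167 or less passes, and one above 0.10 fails, in all three. The choice of family matters only in between.

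- Verdict lost: p = 0.04 with nothing else small passes at m = 2 (0.05) and fails at m = 3 (0.0333) and m = 6 (0.0167).
- Verdict gained: p = 0.08 with the other primary at 0.50 fails at m = 2. At m = 6 with four 21C p-values of 0.001 it ranks fifth and passes (0.08 ≤ 0.0833).

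**2. Chance of a false HSL-control claim on either primary when HSL has no effect** (simulation, 400,000 draws; 21C differs by d on both primaries):

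| d | two tests | three pairs per outcome | six tests |
|---|---|---|---|
| 0 | 10.0% | 8.7% | 4.4% |
| 0.25 | 10.0% | 11.8% | 7.5% |
| 0.5 | 10.0% | 16.4% | 13.4% |
| 0.75 | 10.1% | 18.8% | 15.9% |
| large d (exact limit) | 10.0% | 19.0% | 16.0% |

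The limits can be checked by hand. Three pairs: 1 − 0.9² = 0.19. Six tests: 1 − (1 − 5/60)² + (0.10 − 5/60)² = 0.160. If 21C differs on reading only (d = 0.5), the figures are 12.6% for three pairs and 8.7% for six tests. The six-test rate reaches the 10.0% of the two-test family only at d of about 0.35 on both primaries.

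**3. If p below 0.05 is also required.** Any HSL-control p below 0.05 already passes at m = 2, so sharing a family with 21C can only remove verdicts. The false-claim chance is at most 1 − 0.95² = 9.75% in every reading.

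**4. False discovery rate.** In the six-test family it is 9.3% when nothing differs and 3.2-3.4% when 21C differs. With six null tests the procedure cuts the chance of any false claim from 23.0% to 9.3%.

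**5. How often the reading matters.** Take a true HSL effect on one primary of 0.51 SD, the effect giving 80% power at 0.05. With 21C equal to control, power is 81% (two tests), 82% (three pairs) and 73% (six tests). The table shows how often the three readings disagree on that primary.

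| 21C effect relative to HSL | 21C acts on that primary only | 21C acts on both |
|---|---|---|
| none | 10.3% | 10.3% |
| half | 12.7% | 10.2% |
| same | 10.3% | 5.0% |
| twice | 7.5% | 6.8% |

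All three readings therefore agree in roughly 87-95% of trials.

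**The case for a change.** The strongest case for a change is that the dependence on 21C is real and simple to demonstrate. The false discovery rate of the whole family can be well controlled while the error rate of the one randomised contrast rises to 16-19%, driven by comparisons open to selection. Naming the family would take a few sentences and no new data. Since the document postdates both summers, an unnamed family leaves room to choose after the fact.

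Part of this stands. The family is not named, and a result with p between 0.0167 and 0.10 should be read with that in mind. The rest weighs less:

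- **Size of the 21C difference.** The high false-claim rates need 21C to differ by about 0.5 SD or more on both primaries. The document gives no such value, and the models adjust for baseline score, age, gender, race and year.
- **Real 21C effects.** 21C is itself an academic programme. A genuine 21C difference that raises the cut-off is the procedure working as designed.
- **The 0.05 level.** It is stated for all analyses. Applied alongside the correction, it removes the inflation altogether.
- **Timing.** The concern about late choice is limited by the narrow range of p in which the choice matters. Where unadjusted p-values are reported, a reader can recompute the verdict under any family.

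**Conclusion.** The gap is real, but it is missing detail that an analyst can fill sensibly, and no change to the plan follows. The method and its level are stated. The 0.05 and 10% figures are compatible on the usual reading: 0.05 for single tests, Benjamini-Hochberg where there are several. A 10% rate is defensible in a study sized to estimate parameters for later trials.

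HSL-control alone, three pairs per outcome and all six primary comparisons are each reasonable families, and experienced statisticians would differ over which to prefer. Prescribing one would replace the sponsor's judgement with a preference rather than correct an error.

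The consequence is confined to HSL-control p-values between 0.0167 and 0.10 (two tests against six). Disagreement among the primary-only readings is about 7-13% of trials if 21C acts on one primary and 5-10% if on both. These percentages rest on an assumed 0.51 SD effect, normal data, independent outcomes and a single follow-up. An outcome correlation of 0.3 moves the false-claim rates by less than one percentage point.
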